It should be noted that it is assumed that the average cluster size is 6 in all centers for these calculations. The design effect (DE) concept is used in cluster randomized trials to inflate the sample size of the study, compared to the traditional randomized trials [44]. When cluster size is fixed, $DE = 1 + [(m - 1) \times ICC]$; where m is the average cluster size and ICC is the intraclass correlation coefficient. In other words, the sample size of the study can be calculated by traditional methods, and should be multiplied by the DE. Under the assumption that m = 6 and ICC = 0.01, DE becomes 1.05. To compare 17.8% vs 2.7% surgical complication rates for a (*not clustered*) randomized trial, with 84% power, and 0.05 type I error rate, we would need to enroll 136 patients total. This is also listed in the sample size calculator above under the "unadjusted box". For a DE value of 1.05, this sample size should be multiplied by 1.05 to find the sample size of a cluster randomized trial to reach same power. Therefore, the sample size of the clustered randomized trial would be 136 x 1.05 = 142.8 ~143.

The variable cluster size is common in cluster randomized trials. Eldridge et al considered the effect of variable cluster size on the sample size calculation for cluster randomized trials [45]. They showed that the DE value can be calculated for variable class sizes. DE' = $1 + {(cv^2+1) m - 1} x$ ICC; where cv is the coefficient of variation of cluster sizes (standard deviation of cluster sizes divided by the mean cluster size). The cv is 1.08 for our study. If we use the current average cluster size of m = 2.9, DE' becomes 1.06. In other words, the sample size of the study should be inflated to 136 x 1.06 = 144.16~145 to reach 84% power. This assures us that our planned sample size of 145 patients will allow us to reach 84% power even if our cluster sizes will not be fixed at 6.

It should be noted that, as of March 6th 2018, only 1 of 100 enrolled patients was lost to followup. However, to account for a potential 2% loss to follow up on the 145 subjects needed (72 per group), we will recruit 148 subjects total (74 per group) over the entire trial enrollment period, which is proposed to be extended to December 31, 2018.

Aim 2: Non-Inferiority Margins and Power

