recommended non-inferiority margin of 0.175 units for the clinical improvement outcome is consistent with the FDA-recommended largest acceptable non-inferiority margin of 0.175 units.

In contrast to clinical improvement, syrinx regression is an objectively measurable and easily quantifiable outcome. It is measured by comparing syrinx size on MRI scans obtained before and after surgery. When the effective sample size is 68 subjects per group, and assuming 89.1% syrinx regression rate in the PFDD group [27], the non-inferiority margin is 0.135 units to reach 81% power. A non-inferiority margin of 0.135 units represents no more than 13.5% reduction from the PFDD group in terms of syrinx regression. Note that a one-sided type I error rate of 0.05 was assumed, and the 'Two group test of equivalence in proportions' option in nQuery Advisor was used for the sample size calculations.

Determine if PFD provides non-inferior syrinx regression compared to PFDD (Non-inferiority Design)							
Outcome	PFDD	PFD	Data Source	Non-inferiority Margin	α-level	Subjects per group	Power
Syrinx Regression	261/293 (89.1%)	31/38 (81.2%)	Durham [27] and PRSRC	0.135	0.05	72	81%

For these calculations, the drop-out rate is assumed to be 2%, intra-class correlation coefficient is 0.05, and the onesided type I error rate is 0.05.

Aim 3: Power Calculations

Based on preliminary data using the Chiari Health Index in Pediatrics (CHIP)[50], we observed a 0.12±0.16 unit improvement in Quality of Life (QOL) scores following PFDD. Our sample size of 72/group (effective sample size of 68/group) will provide 82% power to detect a 0.20±0.16 unit improvement in CHIP QOL scores following PFD (α =0.05). Both from an analytical standpoint and from the view of PRSRC investigators and our patient partners, this value represents both a significant and meaningful increase in QOL

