Second Chiari surgeries will be analyzed as 1) the proportion requiring a surgical revision and 2) the type of second surgery performed (same or cross-over). The 1-sided confidence interval for the difference in rates between the PFD and PFDD groups will be calculated and compared to the corresponding non-inferiority margins.

Specific Aim 3:

Hypothesis: With fewer surgical complications, PFD will be associated with superior QOL compared with PFDD.

Anticipated Outcome: PFD will have superior QOL and will show improvements in overall QOL over time (≤ 12 months post-operatively (± 2 months)) compared to PFDD. In particular, both physical metrics (evaluated by pain frequency, pain severity and non-pain symptoms) and psychosocial metrics will improve at a higher rate and in a shorter period of time after PFD compared to PFDD.

Secondary outcomes include Treatment Efficacy variables and Quality of Life variables. Continuous variables measured at 3 time points over the 12-month follow-up will be analyzed using longitudinal analysis with linear mixed models including the random cluster effect. Binomial and ordinal data will be analyzed using Mixed Model methods accounting for cluster. In addition, sensitivity analyses will be conducted where the missing data points will be imputed based on the last observation carried forward.

It should be noted that for Aim 3, primary analyses will be based on the QoL exam performed at 10 to 14-month window. A sensitivity analyses will also be performed based on the last QoL exam available at any time \geq 3 months after surgery. Analyses based on the mixed effect model will also be performed where both cluster effect and error terms will be random.

Missing data: Based on PRSRC data and early data from this trial, loss to follow-up rate is expected to be low (<2%). To prevent missing data, we will meet with patients at 1 month, 3-6 months and at 12+/-2 months after the procedure. Every effort, including phone call reminders to patients, will be made to decrease loss to follow-up. Loss to follow-up, missing data, and the reasons leading to loss of follow-up or data will be recorded. In case of missing data, we will impute missing data using different methods. Because of the repeated measures nature of the data, the 'last observation

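### No Aim 3 model in the SAP includes baseline CHIP or HUI-3, and the plan does not say whether the 10 to 14 month outcome is the score or its change from baseline

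*SAP*

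**What the plan says.** - **Longitudinal model (SAP 7.5, Specific Aim 3).** Continuous outcomes taken at three times during follow-up "will be analyzed using longitudinal analysis with linear mixed models including the random cluster effect". The three times are all post-operative. No fixed effects are listed, not even treatment or visit.
- **Primary Aim 3 analysis (same section).** The "primary analyses will be based on the QoL exam performed at 10 to 14-month window". No model is written for it, and score or change from baseline is not stated. The mixed model is mentioned as a further analysis.
- **Covariates elsewhere in SAP 7.5.** The 6 to 24 month secondary analysis adds time to last follow-up. The subdomain analysis lists medical history, pathology and syrinx variables. The exploratory response model has its own longer list. Baseline CHIP and HUI-3 appear in none of them. Only the Aim 1 GEE formula carries baseline covariates, and they are not named.
- **Response to imbalance (SAP 7.5).** Centre-level summaries are reweighted if prognostic factors are unbalanced.
- **Baseline data.** CHIP and HUI-3 are scheduled at the initial visit (Protocol 6.1, SAP 5.1). SAP 1.2 restricts the CHIP report to fully completed forms.
- **Power (SAP 7.2.1, Aim 3; also Protocol 9.5).** "we observed a 0.12±0.16 unit improvement in Quality of Life (QOL) scores following PFDD", and "Our sample size of 72/group (effective sample size of 68/group) will provide 82% power to detect a 0.20±0.16 unit improvement in CHIP QOL scores" after PFD, with alpha 0.05.

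**The concern.** A patient's starting quality of life usually predicts later quality of life well. Leaving it out of the model gives up precision at no saving in data collection.

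The open recruitment adds to this. Each centre knows its arm before enrolment, families know the procedure when they consent, and patients who do not suit it or are not comfortable with it are not enrolled (Protocol 5.1 and 6.2.2). Baseline CHIP could therefore differ between arms by more than chance. Reweighting centres does not adjust for a patient's own starting score.

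As written, three analyses remain possible for a named superiority aim: follow-up score, change score, or baseline-adjusted score. They differ in power and respond differently to the same baseline imbalance.

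**Working it through.** **Inputs.** Improvement 0.12 (PFDD) and 0.20 (PFD), so the difference is 0.08; change SD 0.16; effective n = 68 per group; alpha 0.05 (SAP 7.2.1, Aim 3). Overall CHIP SD 0.18, 75% of forms complete, test-retest correlation 0.83 (Protocol 7.2.1, Table 4). The baseline to 12-month correlation r is not in the documents.

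**Step 1: reproduce the plan's figure.** SE = 0.16 × √(2/68) = 0.0274, and 0.08/0.0274 = 2.92. Two-sided power is 82.5% by noncentral t (83.0% by normal approximation), matching the stated 82%. One-sided power would be 89.5 to 89.8%, and two-sided power at 72 per group 84.6 to 85.1%. So the plan's figure is two-sided at 68 per group on change scores.

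**Step 2: implied correlation.** Assume SD 0.18 at both times. Change variance = 2 × 0.18² × (1 − r), so r = 1 − 0.16²/(2 × 0.18²) = 1 − 0.0256/0.0648 = 0.605.

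**Step 3: power of the three analyses at 68 per group.** Adjusted SD = 0.18 × √(1 − 0.605²) = 0.143.

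| Analysis | SD | Power |
|---|---|---|
| Follow-up score alone | 0.18 | 73.0% |
| Change score | 0.16 | 82.5% |
| Baseline-adjusted | 0.143 | 89.8% |

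The adjusted variance is 1 − r² = 63% of the follow-up-only variance and (1 + r)/2 = 80% of the change-score variance.

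**Step 4: vary r.** With the change SD held at 0.16, adjusted SD = 0.16 × √((1 + r)/2). With the CHIP SD held at 0.18, adjusted SD = 0.18 × √(1 − r²).

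| r | Adjusted power, change SD 0.16 (change score: 82.5%) | Adjusted power, CHIP SD 0.18 (follow-up alone: 73.0%) |
|---|---|---|
| 0.3 | 94.8% | 76.9% |
| 0.5 | 91.7% | 84.4% |
| 0.605 | 89.8% | 89.8% |
| 0.7 | 88.1% | 95.0% |
| 0.83 | 85.7% | 99.6% |

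The gain over change scores runs from 85.7 − 82.5 = 3.2 to 94.8 − 82.5 = 12.3 points.

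**Step 5: a chance baseline imbalance.** With no clustering beyond the effective n, the SE of the baseline difference is 0.18 × √(2/68) = 0.031. A difference of one SE moves the estimate as follows:
- follow-up score alone: r × 0.031 = +0.019, or 23% of 0.08;
- change score: (r − 1) × 0.031 = −0.012, or 15% of 0.08, in the opposite direction.

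Follow-up scores leave the imbalance in the estimate. Change scores subtract all of it when the slope is only about 0.6, so they over-correct.

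**Step 6: incomplete baseline forms.** As an illustration, if 75% of 68 (51 per group) were usable, power would be 70.6% for change scores and 79.7% with adjustment. Dropping patients with no usable baseline could cost more than adjustment gains.

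**The case against.** The strongest reply is that the SAP is silent rather than opposed. The model sentence omits even treatment and visit, so it is not a complete model from which a baseline term was removed. This stands: a reader might infer that the plan has decided against adjustment, and the text does not show that.

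The documents also lean towards change from baseline. The power text uses improvements, and the aim speaks of QOL improving over time. If change is analysed, baseline already enters by subtraction, and the relevant comparison is 82.5% with about 90%, not 73% with 90%. This also stands, but the SAP never says that change is the outcome, and change scores still lose precision and over-correct.

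Three further inferences are tempting and unsupported:
- **That adjustment removes the bias from open recruitment.** It handles measured baseline QOL only. Selection on other factors remains.
- **That every patient supplies a baseline score.** The tables give a schedule. Only complete forms are used, and 75% were complete in the development data. A change score needs the same baseline value, so this argues for a missing-baseline rule rather than against adjustment.
- **That the trial could have been smaller.** The SAP is dated July 2021 and enrolment was proposed to end in December 2018, so the benefit now is a more precise estimate.

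**Conclusion.** The point holds as a gap in efficiency and pre-specification. No Aim 3 analysis names baseline CHIP or HUI-3, and the form of the primary outcome is not fixed. Adjustment brings power to about 90%, from 82.5% for change scores or 73% for follow-up scores alone, if the CHIP SD is 0.18 at both times. That assumption combines an SD from development data with a change SD from preliminary PFDD data, so r of about 0.6 is inferred. Over r from 0.3 to 0.83 with the change SD at 0.16, the gain over change scores is about 3 to 12 points; its direction does not depend on the value of r in that range.

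A reader might infer that the Aim 3 sample size is wrong. It is not: the stated 82% reproduces and does not rely on baseline adjustment. The change should be made, but the aim does not fail without it.

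**What to change.** In SAP 7.5, Specific Aim 3:

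1. State the outcome of the 10 to 14 month CHIP comparison and write its model: treatment and the patient's baseline CHIP as fixed effects, with the random centre effect.
2. Include baseline CHIP as a fixed covariate in the longitudinal mixed model too. Use baseline HUI-3 for HUI-3.
3. Add a rule for missing or incomplete baseline scores so that no patient is dropped, for example imputation from baseline variables only, or a constrained longitudinal model that treats baseline as one of the repeated measures with a common mean across arms. Carrying the last observation forward cannot fill a missing baseline. The SAP's Buck's regression already uses baseline predictors and could be extended to it.

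The cost is a few sentences, with no new data. The small downside is the extra handling of missing baselines. The choice should be fixed before CHIP is compared by arm.

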Heterogeneity of Treatment Effect (HTE): As an exploratory analyses, to assess if the procedure is most beneficial for a specific subgroup, the heterogeneity of the effect of performing PFDD vs PFD will be assessed within the following pre-determined subgroups based on: 1) patient age at the time of surgery (<5 years, 5-12 years, 13-18 years); 2) CM status (5-12 mm tonsillar ectopia, >12 mm tonsillar ectopia) [39]; 3) syrinx diameter (3-6 mm, 7-9 mm); and 4) preoperative hydrocephalus or neuromuscular disease, two comorbidities associated with increased morbidity following pediatric CM +/- SM surgery [40]. Demographic and comorbidity data will be collected by trained study research assistants/coordinators with strict oversight by site investigators using standard data collection forms. As the 5th subgroup, the effect of surgeon's experience on the occurrence of surgical complications and requirements for re-operations for complications for each procedure during the 1st vs 2nd year of the award period will be assessed. For HTE analysis, the test of procedure (PFD vs PFDD) by subgroup effect (such as age) interaction will be performed to assess the homogeneity of the procedure effect within each subgroup. If the test of interaction indicates a significant interaction for any subgroup, then, Gail and Simon's test of qualitative interaction will be performed [41]. All pre-specified subgroup analyses (patient's age, CM status, syrinx diameter, comorbidity, and surgeons' experience) will be reported regardless of observing a statistically significant or not-significant effect.

Sub-analysis by Syrinx size (3-6 mm, 7-9 mm): A planned subgroup analysis for the syrinx diameter will be performed. Each of the three specific aims will be separately analyzed within the syrinx diameters of 3 to 6 mm and 7 to 9 mm for exploratory purposes. The test of interaction will be used to assess if the treatment effect is homogeneous within each of the syrinx size subgroups (3-6 mm vs 7-9 mm). If the test of interaction indicates heterogeneity, using the whole 3 to 9 mm syrinx diameter range, analyses will be performed, to identify, if any, a cut-off point to propose using one surgical method over the other. For example, whether the PFD is associated with greatly fewer surgical complications when the syrinx diameter is less than 5mm, but surgical complication rates are similar for PFD and PFDD when the syrinx diameter is >6 mm will be examined.

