1.2 Secondary Objectives

Specific Aim 2: Determine if PFD provides non-inferior clinical improvement and syrinx regression compared to PFDD.

Hypothesis: Clinical improvement and syrinx regression provided by PFD will be non-inferior compared to those provided by PFDD.

Anticipated Outcome: Clinical symptoms, neurological function, and syrinx regression ≤ 12 months will be non-inferior following PFD when compared with PFDD.

- Rates of revision decompression surgery (PFD or PFDD) and progression of spinal deformity ≤12 months after PFD also will be non-inferior to PFDD. Please note that the time window is ≤12 months. When there are multiple visits within this window, the visit with the closest to 12 months after surgery will be used.
- For this aim, clinical symptoms and syrinx regression ≤12 months will be used as the primary outcome variable. Results based on the rates of revision decompression surgery and progression of spinal deformity will be exploratory.

Corresponding Variable Names for 'Clinical Improvement'

• Outcome – Scores, Limonadi/Binary -> compare for symptoms and neurological deficits

- Timeframe compare preoperative to:
- ≤ 6 weeks
- 3-6 months
- 12 (+/- 2) months (primary)
- Binary Scoring is primary
- Limonadi Scoring specifics:
- Each subject was given a score for each symptom at each visit, 2=resolved, 1=improved, 0=stable, -1 = worse.
- Symptom scores within a patient were then averaged across visits (per Limonadi paper) to get patient-level symptom-specific scores.
- These patient-level symptom-specific scores were then averaged to get a single overall score per patient.
- These single overall scores per patient were then averaged within site randomization to get group comparisons between sites randomized to PFD and sites randomized to PFDD.
- Binary Scoring specifics:
- Each subject was given a binary score for each symptom at each visit, 1=positive outcome, 0=negative outcome.
- Symptom scores within a patient were then averaged across visits (per Limonadi paper) to get patient-level symptom-specific scores.
- These patient-level symptom-specific scores were then averaged to get a single overall score per patient.
- These single overall scores per patient were then averaged within site randomization to get group comparisons between sites randomized to PFD and sites randomized to PFDD.

Symptoms						
	Double Vision					
	Sensory Symptoms					
	Weakness Symptoms					
	Dysphagia					
	Hoarseness					
	Choking					

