For the purpose of sample size estimation, data from in the Park-Reeves Syringomyelia Research Consortium (PRSRC) were analyzed (ambispective enrollment, n=589 subjects with complete data); specifically, surgical complications ≤ 12 months were used to calculate the sample size. In this dataset, surgical complications were noted in 17.8% of PFDD cases and 2.7% of PFD cases. This is consistent with reported values from a recent meta-analysis, where the rates for CSF-related complications for PFDD and PFD were 18.5% and 1.8%, respectively [27], as well data reported in case series [17, 25] and a systematic review [42]. We expect to observe a similar difference in PFDD versus PFD cases in the proposed study. Because of the clustered randomized nature of the trial, the intraclass correlation coefficient (ICC) should be taken into account. The ICC is defined as the proportion of the between cluster (PRSRC center) variation to the total variation. Since the cluster sizes are small (6 per PRSRC center), and we have a large number of centers available for enrollment (47 total), the effect of ICC on sample size will be small. Thus, using the PRSRC values of 17.8% for PFDD and 2.7% for PFD, and assuming equal number of subjects per group and twosided type I error rate of 0.05, to reach 90% power, 36 centers averaging 6 subjects per center will be required for the trial assuming the ICC is 0.05. To account for 2% dropout rate, we originally planned to recruit 40 centers with a cluster size averaging 6 subjects with overall sample size of enrolled patients of 240 patients, approximately 120 patients per procedure over the two years of enrollment.

Aim 1: Sample Size Recalculation (November 29, 2017)

The original sample size calculation was performed based on surgical complication rates (≤ 12 months) from Park-Reeves Syringomyelia Research Consortium (PRSRC) estimates (17.8% in PFDD and 2.7% in PFD cases). We originally did not have an estimate for the ICC. Based on the literature, we assumed ICC of 0.05 in our calculations [43]. The overall sample size of enrolled patients would be 240 patients, approximately 120 patients per procedure over the two years of enrollment.

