carried forward' method will be utilized [37]. In addition, Buck's method, which is the extended version of regression imputation, will be used [38]. The Buck's imputation will be based on the observed values of patient's age, CM (\geq 5mm tonsillar ectopia), syrinx diameter, and pre-operative comorbidities. In addition to the overall rates of missing data for each procedure, because of the cluster randomized trial, we will also monitor the missing data within each cluster and center and report the discrepancy between the loss to follow-up rates for each procedure. Special attention will be given and separately reported if the entire cluster is loss to follow-up. As a sensitivity analysis for the missing data, study results will be compared for the following three conditions: 1) patients with missing primary outcome variable are excluded from analyses; 2) results with last observation carried forward, and 3) results with Buck's method. Robustness of the results under each scenario will be assessed.

Heterogeneity of Treatment Effect (HTE): As an exploratory analyses, to assess if the procedure is most beneficial for a specific subgroup, the heterogeneity of the effect of performing PFDD vs PFD will be assessed within the following pre-determined subgroups based on: 1) patient age at the time of surgery (<5 years, 5-12 years, 13-18 years); 2) CM status (5-12 mm tonsillar ectopia, >12 mm tonsillar ectopia) [39]; 3) syrinx diameter (3-6 mm, 7-9 mm); and 4) preoperative hydrocephalus or neuromuscular disease, two comorbidities associated with increased morbidity following pediatric CM +/- SM surgery [40]. Demographic and comorbidity data will be collected by trained study research assistants/coordinators with strict oversight by site investigators using standard data collection forms. For HTE analysis, the test of procedure (PFD vs PFDD) by subgroup effect (such as age) interaction will be performed to assess the homogeneity of the procedure effect within each subgroup. All pre-specified subgroup analyses (patient's age, CM status, syrinx diameter, comorbidity, and surgeons' experience) will be reported regardless of observing a statistically significant or not-significant effect.

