Sub-analysis by Syrinx size (3-6 mm, 7-9 mm): A planned subgroup analysis for each of the 3 to 6 mm and 7 to 9 mm syrinx diameters will be performed for each of the 3 aims. The test of interaction will be used to assess if the treatment effect is homogeneous within each of the syrinx size subgroups (3- 6 mm vs 7-9 mm). If the test of interaction indicates heterogeneity, using the whole 3 to 9 mm syrinx diameter range, analyses will be performed, to identify, if any, a cut-off point to propose using one surgical method over the other. For example, whether the PFD is associated with greatly fewer surgical complications when the syrinx diameter is less than 5mm, but surgical complication rates are similar for PFD and PFDD when the syrinx diameter is \geq 6 mm will be examined.

Secondary Analysis

The aims will be evaluated using the overall population who were followed from 6 months to 24 months after enrollment. Analysis will be performed to compare the per Treatment groups for time to last follow-up in order to determine if there is differential follow-up times between groups. Analysis of Aims 2 and 3 will be similar to the primary analysis with adjustment for time to last follow-up as a covariate.

Aim 3 includes some questions that may not be applicable for younger children. For example, keeping up with schoolwork or difficulty with math. Therefore, for this ,a subgroup analysis for

those children age >5 years will also be performed. Additional analysis will include subdomain comparisons of: Pain symptoms Headache Back pain Non-pain symptoms Difficulty raising arms Difficulty walking Frequently lose balance Psychosocial Tired Easily frustrated Trouble sleeping Difficulty concentrating Difficulty paying attention in class Forgetful Difficulty with reading Difficulty with math Difficulty learning new things Difficulty keeping up with schoolwork. Covariates in this analysis will include medical history (Autism, ADHD, Known Psych Disease),

pathology (known Craniofacial Anomalies, Known Skull Malformation, Known Hydrocephalus, Known Spine Column Disorder) and Syrinx (Syrinx Level Known, Syrinx AP Diameter).

Exploratory Analysis

Additional exploratory subgroup analyses will be performed for Aims 2 and 3. These analyses will include age (<5,5-12,13-18), CM status (5-12,>12 mm), and preoperative hydrocephalus or neuromuscular disease. These analyses will examine if there is differential response between the groups.

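### The syrinx-size sub-analysis can lead to an unspecified, uncorrected search for a diameter cut-off meant to favour one operation; a false start is uncommon, but after one the search usually yields a cut-off and an inflated effect

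*SAP*

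**What the plan says.** SAP 7.5, Sub-analysis by Syrinx size, states that separate analyses by syrinx group "syrinx diameters will be performed for each of the 3 aims". The next step depends on the interaction test pointing to a difference in effect between the two groups. In that case the search covers all eligible diameters, and the SAP gives its purpose: "analyses will be performed, to identify, if any, a cut-off point to propose using one surgical method over the other". As an illustration, it describes a large PFD advantage in complications under 5 mm and little difference at larger diameters. The larger group starts at 6 mm inclusive in the SAP but strictly above 6 mm in Protocol 9.5, and both leave out part of the range between 5 and 6 mm.

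On status, the Protocol says each aim will be "separately analyzed within the syrinx diameters of 3 to 6 mm and 7 to 9 mm for exploratory purposes". The SAP's syrinx paragraph does not repeat this. The SAP paragraph just before it, on heterogeneity of treatment effect, lists syrinx diameter among its subgroups and opens "As an exploratory analyses, to assess if the procedure is most beneficial for a specific subgroup".

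Neither document gives a significance level for the interaction test, candidate cut-offs, a criterion for choosing among them, an adjustment over aims or cut-offs, a correction for optimism, a validation step, or an interval for the cut-off.

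**The concern.** A cut-off chosen because it gives the sharpest contrast in the data looks sharper than it is. The worked example adds a second problem. It contrasts a large difference on one side with similar rates on the other, and with few events similar rates may only mean that too few patients had a complication.

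The stated use raises the stakes. The cut-off is meant to support choosing one operation over the other, and Protocol section 13 plans a consensus conference to draft surgical guidelines from the results. A diameter rule from an unplanned search could reach those guidelines with an inflated effect on the favoured side and no stated error rate.

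**Working it through.** **Inputs.** Complication rates of 17.8% (PFDD) and 2.7% (PFD) and 72 patients per group come from SAP 7.2.1. The two lead outcomes of Aim 2 come from SAP 1.2: "clinical symptoms and syrinx regression ≤12 months will be used as the primary outcome variable". The only relevant level is the "twosided type I error rate of 0.05" used to size Aim 1. None is given for the interaction test, so 0.05 is an assumption, with 0.10 shown as a range.

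**The plan's own figure.** Per-group size for an unclustered comparison at 84% power:

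n = [1.960 × √(2 × 0.1025 × 0.8975) + 0.994 × √(0.178 × 0.822 + 0.027 × 0.973)]² / 0.151² = 69

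That is 138 in total, against the stated 136. The planning figures reproduce.

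**Events available.** 72 × 0.178 = 12.8 and 72 × 0.027 = 1.9, so about 15 complications. If diameters are spread evenly over whole millimetres 3 to 9, three sevenths of each arm (about 31 patients) fall in 7-9 mm. This gives about 31 × 0.178 = 5.5 PFDD events and 31 × 0.027 = 0.8 PFD events. A non-significant difference there says little about similarity.

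**How often the search starts in error.** Trials were simulated with the same effect at every diameter, 72 per arm, diameters uniform over the range and no clustering. The interaction compared 3-6 with 7-9 mm at p<0.05, using risk differences for binary outcomes and equal arms for Aim 2.

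| Outcome | False interaction |
|---|---|
| Complications | 4.2% to about 6%, depending on the variance estimate |
| Clinical improvement | 5.0% to 5.6% |
| Syrinx regression | 3.9% to 4.5% |
| CHIP | 5.2% to 5.5% |

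For complications on the log-odds scale, the link that SAP 7.5 names for Aim 1, the figure is about 0.5%. At a level of 0.10 on the risk-difference scale it is about 11%.

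At least one false start, with tests taken as independent:
- three aims: 1 − 0.95³ = 14.3% (27.1% at 0.10)
- four lead outcomes: 1 − 0.95⁴ = 18.5% (34.4% at 0.10)

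**What the search finds after a false start.**
- If it takes the smallest interaction p-value over a set that includes the 7 mm split, it returns a nominally significant cut-off every time, by construction. In 38% to 60% of these trials the best cut-off is not 7 mm.
- The SAP's illustration for complications can be read as PFD better below (Fisher p<0.05) and no difference above (p≥0.05). About 79% of falsely started trials then show it at one or more cut-offs from 4 to 9 mm.
- In those falsely started trials the larger of the two subgroup effects averages about -26 points and the smaller about -4. The true effect is 2.7 − 17.8 = -15.1 points in both.

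**Both steps together, complications.** About 0.06 × 0.79 = 4.7% of constant-effect trials start falsely and show the pattern.

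**The case against.** The best defence is that the plan is more guarded than it first looks. The search is conditional on an interaction test, the text allows that no cut-off may exist, and the analysis is labelled exploratory. The split has a basis: the Protocol (7.2.1, Figure 3) reports 6 mm as a critical diameter for clinical outcome. The below-5 mm contrast is only an example, no p-value rule is written, and using the whole range does not exclude modelling diameter as continuous.

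Most of this stands, and it rules out two stronger readings. A reader might infer that the plan will produce a cut-off in most trials even when the effect is constant, because searching without the interaction test gives the pattern in about 80% of simulated trials. That is not the plan's error rate. It omits the test that must come first, and much of it comes from high cut-offs, where the group below is most of the sample and simply shows the true overall effect. A reader might also infer that the SAP dropped the exploratory status stated in the Protocol. It did not: its heterogeneity paragraph gives that status to the subgroup analyses, syrinx diameter included. The syrinx paragraph only fails to repeat it.

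The defence does not supply the missing level, selection rule or correction. Nor does an exploratory label fit an output intended to propose an operation.

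**Conclusion.** The point holds as an inexpensive improvement to an exploratory analysis; it does not threaten the primary comparison. Under a constant effect the search starts falsely in about 6% of trials or fewer per outcome, and in about 14% over three aims. Positively correlated outcomes would lower the 14%; testing at 0.10 would raise it. Once falsely started on complications, the search usually returns a cut-off, with the larger subgroup effect at about -26 points against a true -15.

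These sizes rest on assumptions the documents do not settle: the 0.05 level, evenly spread diameters, no clustering, the risk-difference scale, and reading the illustration as significant below and non-significant above. The log-odds scale makes false starts on complications much rarer. The absence of a stated level, selection rule and correction does not depend on any of these assumptions.

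**What to change.** Replace the cut-off search in SAP 7.5 with a pre-specified treatment-by-diameter interaction for each aim, with diameter continuous and clustering by center accounted for. State the form of the diameter term, the level of the interaction test and how the three aims are handled together. Show the estimated PFD-PFDD difference across 3-9 mm with confidence bands. For complications the bands will be wide, which is the honest picture with about 15 events.

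Repeat the exploratory label in the syrinx paragraph, describe the result as hypothesis-generating, and remove the aim of proposing an operation from it. Reconcile the upper bound of the example between the SAP and the Protocol, or delete the example.

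The change uses data already collected and costs only SAP wording. The downside is that no simple threshold is reported. If a cut-off must be kept, the SAP should list the candidates and the selection criterion and give a bootstrap- or permutation-corrected cut-off with an interval, still as hypothesis-generating.
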